5.1. Overall Design

Study CGAN is a multisite, randomized, double-blind, placebo-controlled bridging study of galcanezumab in Japanese outpatients suffering from migraine. The study has 4 periods, including a prospective baseline phase to determine patient eligibility. Patients who complete Study Period III may have an option to roll-over to the open-label extension study, I5Q-JE-CGAP (CGAP). [Figure CGAN.5.1](#) illustrates the study design.

^aEligibility period determined between a minimum of 30 days and a maximum of 40 days. Investigators may have up to 5 additional days (beyond the 40 days) if needed to schedule patients' Visit 3 appointment.

^aPatients randomized to the 120 mg dose will receive a loading dose of 240 mg at the first injection only (Visit 3).

Approximately 240 enrolled patients roll-over to I5Q-JE-CGAP study (Open Label Extension) at visit 12

Abbreviations: SP = study period.

Figure CGAN.5.1. Illustration of study design for Study I5Q-JE-CGAN.

Study Period I: The study and potential risks for both study I5Q-JE-CGAN and I5Q-JE-CGAP will be explained to the patient at Visit 1. The informed consent form (ICF) must be signed before any study procedures are performed. Patients are required to discontinue all excluded medications or migraine-prevention treatments at least 30 days prior to Visit 2. Botulinum toxin A or B in the head or neck area must be discontinued at least 4 months prior to Visit 2.

The screening visit (Visit 1) will consist of a full clinical assessment, including a comprehensive medical evaluation documenting medical history, and a physical and neurological examination (Section 2). Visit 1 will be complete when the last scheduled procedure of the screening assessment is completed.

Study Period II: Qualified patients will enter Study Period II (prospective baseline) to determine their eligibility for the study, and to establish baseline data for comparison of endpoints during the treatment period. Beginning at Visit 2, patients will log in daily to the electronic patient-reported outcomes (ePRO) system to answer questions about the occurrence of headaches, headache duration, headache features, severity of headache, and use of headache medication. At the end of the prospective baseline period, sites will be notified whether their patients met the criteria and are eligible to be randomized to treatment at Visit 3.

To avoid biased reporting, patients must not be told the number of migraine headache days on which study qualification is based.

Study Period III: At the start of the 6-month, double-blind treatment phase (Visit 3), patients meeting all eligibility requirements will be randomized to 1 of 3 treatment groups in a 2:1:1 ratio to receive placebo, 120 mg/month galcanezumab, or 240 mg/month galcanezumab, respectively.

Patients randomized to the 120 mg dose of galcanezumab will receive an initial loading dose of 240 mg (2 injections of 120 mg each at Visit 3 only). To preserve blinding throughout the study, patients in all treatment groups will receive 2 injections of investigational product at each dosing visit. At Visit 3, if available and where local regulations in Japan and ethical review boards/institutional review boards (ERBs/IRBs) allow, patients will also watch a training video designed to address patient expectations with regard to participation in a placebo-controlled trial, and the difference between medical treatment and research.

The patient will be considered enrolled in the study when randomization occurs. During this phase, study procedures at dosing visits must always occur prior to the patient receiving his/her assigned treatment of study drug.

Patients will be given injections of study drug during office visits ([Figure CGAN.5.1](#)). For all treatment groups, subcutaneous injections will be administered once monthly at the dosing visits. At Visit 3 (first dose), patients will be required to remain at the site for observation for at least 30 minutes post-injection. Following subsequent doses, patients will be observed for at least 30 minutes post-injection if they have a significant adverse event after the first injection and/or they are judged by the investigator to have risk of a significant adverse event after injection. Patients will continue to log in and complete the ePRO diary each day. Patients may continue to take their allowed acute migraine headache medication (with some limitations; see concomitant medication study tool) during the treatment phase.

Patients who do not participate in the CGAP study and who complete Study Period III, or who discontinue for any reason during Study Period III, will be expected to enter post-treatment follow-up (Study Period IV).

Patients who discontinue for any reason during Study Period III will be expected to take the measurement for Early Termination (ET).

Study Period IV: Only patients who do not participate in the CGAP study will move on to Study Period IV. During this 4-month phase, sites and patients will remain blinded to patients' treatment assignments. Patients will follow all study procedures during Study Period IV, but will

not receive galcanezumab or placebo. One month after Visit 12, if clinically warranted due to a worsening of symptoms, patients may start migraine prevention medications at the discretion of the investigator. The list of allowed preventive medications is provided in the concomitant medication study tool. At Visit 14 (Month 10), patients will return to the site for their last study visit and discharge from the study.

Patients who discontinue for any reason during Study Period IV will be expected to take the measurement for ET.

5.2. Number of Participants

Approximately 902 participants will be screened to achieve 451 randomized participants for an estimated total of 225 evaluable participants in the placebo group and 113 evaluable participants each in the galcanezumab (120 mg and 240 mg) treatment groups.

5.3. End-of-Study Definition

End of the trial is the date of the last visit or last scheduled procedure shown in the Schedule of Activities (Section 2) for the last patient.

5.4. Scientific Rationale for Study Design

The length of the randomized treatment phase is considered sufficient to assess the safety and efficacy of a migraine prevention medication, and is consistent with Studies CGAH/CGAG. A 4-month, post-treatment follow-up phase is included to evaluate patient safety during wash-out of galcanezumab. This allows for a total of 5 months of observation from the time of last injection of galcanezumab. A 5-month, post-treatment observation period allows for a wash-out of approximately 5 elimination half-lives of galcanezumab, and should decrease galcanezumab serum concentrations by approximately 97% during this time. For the roll-over patients, a 5-month, post-treatment observation period will be conducted after treatment for an additional 12 months in Study CGAP.

5.5. Justification for Dose

This study is a bridging study with 2 global Phase 3 studies (I5Q-MC-CGAG [CGAG] and I5Q-MC-CGAH [CGAH]). Therefore, the doses selected for this study were the same doses used in Studies CGAG and CGAH. In Studies CGAG and CGAH, doses of 120 mg and 240 mg galcanezumab administered once monthly were selected primarily on the basis of clinical efficacy and PK/PD data from the Phase 2 dose-ranging study, I5Q-MC-CGAB (CGAB). Results from Study CGAB indicated that 120 mg was statistically significantly superior to placebo at the last 28-day period of the 3-month treatment phase in mean change in migraine headache days, as well as in other measures of efficacy and quality of life. The use of a loading dose for the 120-mg treatment arm, and the inclusion of a 240-mg treatment arm, is based on the finding that a dose higher than 120 mg achieved statistically significant separation from placebo as early as Month 1.

In the Phase 1 study (Study I5Q-MC-CGAE [CGAE]), single doses of galcanezumab up to 300 mg and three every-4-week (Q4W) 300-mg doses of galcanezumab were well tolerated in both Japanese and Caucasian subjects.

6. Study Population

All patients must meet the following selection criteria. Eligibility of patients for study enrollment will be based on the results of a screening medical history, physical examination, neurological examination, clinical laboratory tests, ECGs, and migraine history during screening and a prospective baseline period, as described in the Inclusion (Section 6.1) and Exclusion (Section 6.2) Criteria. The nature of any comorbid conditions present at the time of the physical examination and any preexisting conditions must be documented. Individuals who do not meet the criteria for participation in this study (screen failure) for specific reasons, as outlined, may be considered for rescreening once, with approval from Eli Lilly and Company (Lilly) Medical (Section 6.4). Study participants should be instructed not to donate blood or blood products during the study or for 5 months following last administration of investigational product. Prospective approval of protocol deviations to recruitment and enrollment criteria, also known as protocol waivers or exemptions, are not permitted.

6.1. Inclusion Criteria

Patients are eligible to be included in the study only if they meet all of the following criteria at screening:

Patient and Disease Characteristics

- [1] Patients are 18 to 65 years of age (inclusive) at the time of screening.
- [2] Have a diagnosis of migraine as defined by International Headache Society (IHS) International Classification of Headache Disorders- (ICHD-) 3 beta guidelines (1.1 or 1.2) (HCCIHS 2013), with a history of migraine headaches of at least 1 year prior to Visit 1, and migraine onset prior to age 50.
- [3] Prior to Visit 1, have a history of 4 to 14 migraine headache days, and at least 2 migraine attacks per month, on average, within the past 3 months.
- [4] From Visit 2 to Visit 3 (prospective baseline period), have a frequency of 4 to 14 migraine headache days, and at least 2 migraine attacks per month. **To avoid biased reporting, patients must not be told the number of migraine headache days on which study qualification is based.**
- [5] From Visit 2 to Visit 3 (prospective baseline period), must achieve sufficient compliance with ePRO daily headache entries, as demonstrated by completion of at least 80% of daily diary entries.

Informed Consent and Patient Agreements

- [6] Are able and willing to give signed informed consent, and in the case of patients under 20 years old, informed consent signed by a parent or guardian.
- [7] Are reliable and willing to follow study procedures, including all follow-up visits.

- [8] Women of childbearing potential must test negative for pregnancy at the time of enrollment, based on a serum pregnancy test. Women of non-childbearing potential are defined as follows:
- 1) Confirmed spontaneous amenorrhea with evidence of cessation of menses for at least 12 months and a follicle-stimulating hormone(FSH) level >40 mIU/mL at screening,
 - Or
 - 2) Confirmed from medical record to be infertile due to congenital or acquired condition (i.e. hysterectomy or bilateral oophorectomy),
 - Or
 - 3) Confirmed that all partners have had a vasectomy or tubal ligation AND have no fertile sperm based on multiple semen examinations, as shown by their medical record.
- [9] All patients must agree to use a reliable method of birth control during the study, as well as for 5 months after the last dose of investigational product. Acceptable methods of birth control for this study are 1) combination of condom and oral contraceptives, 2) combination of condom and hormonal releasing intrauterine system (IUS), or 3) combination of condom and copper intrauterine device (IUD). These contraception methods are not required for female patients of non-childbearing potential, defined in inclusion criterion [8], or for male patients who meet the criterion defined in definition 3) of inclusion criterion [8].
- [10] Agree not to post any personal medical data related to the study or information related to the study on any website or social media site (for example, Facebook, Twitter, LINE, Mixi, etc.) until the entire trial has completed.

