Study Period (SP)	SP I- Screening	SP II- Prospective Baseline	SP III – Treatment										SP IV – Follow-up	
			30- 45	14	16	30	30	30	15	15	15	15	60	60
(Target) Interval (days) since previous visit														
Allowable range (days) between visits	3-45	30-40 ^a												
Interval allowance (days) compared from previous visit				± 1	± 3	± 2	± 2	± 2	± 2	± 2	± 2	± 2	± 5	± 5
Visit	1	2	3	4 ^b	5	6	7	8	9 ^c	10	11 ^c	12/ET	13	14/ET
Month			0	0.5	1	2	3	4	4.5	5	5.5	6	8	10
Informed consent	X													
Inclusion/exclusion	X	X	X											
Demographics	X													
Physical examination ^d	X													
Height	X													
Weight	X											X		X
Waist and hip circumference	X													
Medical history	X													
Pre-specified migraine history		X												
Substance use	X													
Prior Therapy (Migraine Medication)	X													
ECG ^e	X		X									X		X
Vital signs ^f	X		X		X	X	X	X		X		X	X	X
Adverse events	X	X	X	X	X	X	X	X	X	X	X	X	X	X
Concomitant medications	X	X	X	X	X	X	X	X	X	X	X	X	X	X
ePRO training		X												
ePRO daily patient entries ^g		X	X	X	X	X	X	X	X	X	X	X	X	X
Patient training video			X											
Hematology	X		X				X					X		X
Clinical chemistry	X		X				X					X		X

Study Period (SP)	SP I- Screening	SP II- Prospective Baseline	SP III – Treatment										SP IV – Follow-up	
			30-45	14	16	30	30	30	15	15	15	15	60	60
(Target) Interval (days) since previous visit			30-45	14	16	30	30	30	15	15	15	15	60	60
Allowable range (days) between visits	3-45	30-40 ^a												
Interval allowance (days) compared from previous visit				± 1	± 3	± 2	± 2	± 2	± 2	± 2	± 2	± 2	± 5	± 5
Visit	1	2	3	4 ^b	5	6	7	8	9 ^c	10	11 ^c	12/ET	13	14/ET
Month			0	0.5	1	2	3	4	4.5	5	5.5	6	8	10
HbA1c			X									X		X
Urinalysis ^h	X		X									X		X
Serum Pregnancy (for women of childbearing potential) ⁱ or FSH at Visit 1 (for women who have evidence of cessation of menses for at least 12 months)	X											X		X
Urine pregnancy ^j			X		X	X	X	X		X		X ^m		
Urine drug screen	X													
Immunogenicity ^j			X	X	X	X	X					X		X
Biomarker storage sample ^j			X		X		X			X		X ^m		X
CCI [REDACTED]		X	X	X	X	X	X	X	X	X	X	X	X	X
PK blood sample ^j				X	X	X	X	X	X	X	X	X	X	X
CCI [REDACTED]			X											
Whole blood RNA/epigenetic sample ^j			X									X		X
Study drug administered ^k			X		X	X	X	X		X				
MIDAS			X				X					X		X
MSQ v2.1			X		X	X	X	X		X		X		X
PGI-S			X		X	X	X	X		X		X		X
PGI-I					X	X	X	X		X		X		X

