- ^d Physical examinations at screening must include a neurological exam.
- ^e Electrocardiograms as single, 12-lead digital will be performed at Visit 1, Visit 3, Visit 12, and Visit 14 or ET. Note: The Visit 3 ECG should be collected prior to blood draws and dosing. Patients must be supine for approximately 5 to 10 minutes before ECG collection, and remain supine, but awake, during ECG collection. For screening only, ECG results will be read locally.
- ^f Vital signs will include body temperature, blood pressure, and pulse. Blood pressure and pulse will be measured in triplicate, in the sitting position, and should be measured prior to blood draws. Blood pressure will be assessed by utilizing a calibrated machine.

- ^e Patient enter into the ePRO diary the occurrence of headaches, headache duration, headache features, severity of headache, and use of headache medication
- ^h In the event of a positive urine leukocyte esterase result, a repeat urine sample will be collected at the next visit and shipped to the central laboratory.
- ⁱ A positive urine test must be followed by a serum pregnancy test for confirmation.
- ^j Biomarker storage samples, immunogenicity, CCI ██████████ PK sampling, and whole blood RNA/epigenetic sample to be performed at the indicated visits and prior to dose administration if the visit is a dosing visit. Samples will be taken in the event of ET. Immunogenicity and PK samples also may be collected in the event of a systemic allergic/hypersensitivity reaction (see Section 9.4.3). The timing of samples will be recorded.
- ^k Patients will receive injections of placebo or galcanezumab after all other visit procedures are completed. Following the first dose at Visit 3, patients will be observed for at least 30 minutes at the site. Following subsequent doses, patients will be observed for at least 30 minutes post-injection if they have a significant adverse event after the first injection and/or they are judged by the investigator to have risk of a significant adverse event after injection.
- ^l The C-SSRS and SHSF (and SHSU, when applicable) will be completed at scheduled and unscheduled office visits.
- ^m Urine pregnancy and biomarker storage sample are collected only for patients rolling over to Study CGAP.

3. Introduction

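### Definition 3 of inclusion criterion [8] leaves a possibly fertile woman who does not enter CGAP with no scheduled pregnancy test after her last dose

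*Protocol*

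**What the plan says.** Criterion [8] in Protocol Section 6.1 opens with "Women of childbearing potential must test negative for pregnancy at the time of enrollment, based on a serum pregnancy test". It then lists three ways in which a woman counts as of non-childbearing potential. The first two concern her own body: cessation of menses with a raised FSH, or infertility from a congenital or acquired condition. The third concerns only her partners: "Confirmed that all partners have had a vasectomy or tubal ligation AND have no fertile sperm based on multiple semen examinations", supported by their medical record.

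That status has two consequences.

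- **Contraception.** Criterion [9] requires reliable birth control during the study "as well as for 5 months after the last dose of investigational product", and exempts women of non-childbearing potential as defined in [8].
- **Testing.** In the Schedule of Activities (Protocol Section 2), the serum row is labelled "Serum Pregnancy (for women of childbearing potential") and is marked at Visits 1, 12/ET and 14/ET. Its alternative, FSH at Visit 1, is for women whose menses have stopped.

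The urine row names no population. It is marked at the six dosing visits (3, 5, 6, 7, 8 and 10) and at Visit 12, where footnote m applies: "Urine pregnancy and biomarker storage sample are collected only for patients rolling over to Study CGAP". On the order of procedures at dosing visits, footnote k says: "Patients will receive injections of placebo or galcanezumab after all other visit procedures are completed".

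**The concern.** Sterile partners are a reason to waive contraception. They do not make a woman infertile. Criterion [9] already uses definition 3 in the first sense when it applies it to male patients. Because [8] also files it under non-childbearing potential, one fact about the partners removes both the contraception duty and every serum pregnancy test.

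At stake is the detection of pregnancy during wash-out. Protocol Section 5.4 says the follow-up phase exists to evaluate safety while the drug clears, and Section 9.2.1 sends pregnancies during exposure through the SAE reporting process. A scheduled test is the systematic way to find them. No endpoint, analysis or randomization feature is affected.

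**Working it through.** **Inputs** (Protocol Section 2 unless stated)

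- Target intervals: Visit 10 to 11, 15 days; 11 to 12, 15; 12 to 13, 60; 13 to 14, 60.
- Visit allowances: ±2, ±2, ±5 and ±5 days respectively.
- Last dose at Visit 10 (SAP Section 5.5.5).
- Stated observation time after the last injection: 5 months, about 5 half-lives, about 97% cleared (Protocol Section 5.4).

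**Step 1. Reproduce the plan's own figures.** Visit 10 to Visit 14 = 15 + 15 + 60 + 60 = 150 days, and 150 / 30 = 5.0 months. Five half-lives clear 1 − 0.5^5 = 0.969. Both agree with Section 5.4.

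**Step 2. Apply the windows.** 2 + 2 + 5 + 5 = 14 days, so the interval runs from 150 − 14 = 136 to 150 + 14 = 164 days.

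**Step 3. Count scheduled tests for a woman who completes treatment and, unless she rolls over, follow-up.** The Visit 10 urine test precedes the injection, so it does not count as a test after the last dose. 'Definition 3 only' means that she meets neither definition 1 nor definition 2.

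| Patient | Serum visits | Urine visits | Total | After last dose |
|---|---|---|---|---|
| Childbearing potential, no CGAP | 1, 12, 14 | 3, 5, 6, 7, 8, 10 | 9 | 2 |
| Definition 3 only, no CGAP | none | 3, 5, 6, 7, 8, 10 | 6 | 0 |
| Definition 3 only, enters CGAP | none | 3, 5, 6, 7, 8, 10, 12 | 7 | 1 |

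**Step 4. Locate the two missing tests.** They are at Visit 12, 15 + 15 = 30 days after the last dose, and at Visit 14, 150 days after it. If 150 days is about 5 half-lives, 30 days is about one. Assuming first-order decline, roughly half the drug present at the last dose remains at Visit 12.

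**Step 5. Longest stretch after the last dose without a scheduled test, no CGAP.** Childbearing potential: Visit 12 to 14 = 60 + 60 = 120 days (110 to 130). Definition 3 only: 150 days (136 to 164), with no test at the end of it.

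**Scale.** Protocol Section 10.1 expects 383 completers, and Section 7.8.1 expects about 240 to enter CGAP. That leaves about 383 − 240 = 143 completers of either sex who do not roll over. How many of them are definition 3 women is not stated and could be none.

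**The case against.** The best defence is that this is a deliberate, proportionate choice. Definition 3 is demanding: it covers all partners and needs sterilisation plus repeated semen examinations, shown by medical record. Exclusion [28] bars pregnant women, and a urine test precedes every dose. Adverse events are reviewed at every later visit, pregnancies are reportable however they are found, and Appendix 2 lets the investigator repeat a pregnancy test. The longest untested stretch grows by only 150 − 120 = 30 days, and the later of the two missing tests falls when about 97% of the drug is gone.

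Most of this stands as a reason to rate the point low. It does not close the gap. Repeat tests are discretionary, and a label of non-childbearing potential gives a site little reason to order one. Appendix 5 says [8] and [9] were changed to clarify eligibility, and neither document gives a reason for testing these women less.

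Four stronger readings are tempting, but the documents do not carry them.

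- **That [8] demands a serum test at Visit 3 and the Schedule omits it.** Section 5.1 does equate enrollment with randomization. But Section 6.1 opens by applying the criteria at screening, which fits the Visit 1 serum test, and urine is tested at Visit 3 before dosing. This is wording only.
- **That partner status is singled out for no re-check.** The row "Inclusion/exclusion" ends at Visit 3 for every patient, and no row schedules a check of anyone's contraception. A woman with a new fertile partner no longer meets definition 3.
- **That she has no pregnancy test at all.** This needs the urine row to be limited to women of childbearing potential, and its label sets no such limit.
- **That the same gap certainly applies to women who stop early.** They cannot enter CGAP, so it may. But the urine row's footnote letter is uncertain: i concerns serum confirmation, whereas j has samples taken at early termination. I do not rely on it.

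**Conclusion.** The point holds, as a minor one. A woman who qualifies under definition 3 alone, completes treatment and does not enter CGAP has 0 scheduled pregnancy tests after her last dose, where a woman classed as of childbearing potential has 2. The gap covers the full 150 target days (136 to 164) of wash-out. She also misses the Visit 1 serum test.

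This rests on reading the urine row as covering all women, as its label implies, and on counting scheduled tests only. It does not show that a pregnant woman could be dosed unnoticed: urine is tested before each injection, and the gap starts after the last one. The gain from closing it is a small improvement in detecting pregnancies during wash-out, in a group of unknown size.

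**What to change.** Delete definition 3 from the non-childbearing definition in [8], and state it in [9] as a contraception exemption only. Word it separately for each sex, because the present text joins tubal ligation to semen findings and does not fit a male patient with female partners:

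- **Female patients:** all partners vasectomised, with no fertile sperm on repeated semen examinations, documented.
- **Male patients:** own documented sterility, or all partners of non-childbearing potential or with tubal ligation.

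Women with sterile partners then stay in the existing serum tests at Visits 1, 12/ET and 14/ET and keep their exemption from contraception. Completers who do not enter CGAP go from 6 to 9 scheduled tests, and from 0 to 2 after the last dose.

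The cost is a wording amendment and at most 3 serum assays per affected woman, at visits that already draw blood for hematology and chemistry. No visit is added, and the SAP does not change.
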